11.0 STATISTICAL METHODS AND DATA ANALYSIS

11.1 **Trial Design Considerations**

An open label dose finding study, stratified by disease severity is an appropriate design to assess the safety and tolerability of DUR-928 in this patient population.

11.2 Sample Size Determination

No formal sample size estimates were performed. The number of patients planned for this study is consistent with trials of this design and objectives.

11.3 Patient Randomization

N/A. This is an open label study.

11.4 **Definition of Analysis Population**

The primary analysis set for all safety analyses will be the Intent-to-Treat (ITT) set, which is defined as all enrolled patients who received at least one dose of study drug (DUR-928).

The PK evaluable data set is defined as including those patients who have met criteria for analysis defined in the SAP.

Additional details about the analysis plan, including how missing data will be handled, will be specified in the Statistical Analysis Plan.

11.5 General Statistical Analysis Considerations

The primary objective of this study is to assess dose-related safety and tolerability of DUR-928, with secondary objectives of assessing PK and dose-related evidence of potential efficacy of DUR-928. Study results for dose-related safety, efficacy, and PK profiles will utilize descriptive statistics.

Due to the small number of patients expected to be enrolled at each center, all summaries and analyses will be performed using data pooled across centers. Unless otherwise specified, continuous variables will be summarized by treatment cohort (DUR-928 dose levels) using the ITT analysis set with the number of non-missing observations, mean, standard deviation, median, 25th and 75th percentile, min, and max displayed. Categorical variables will be summarized by DUR-928 dose level using the ITT analysis set as counts and percentages. Missing data will not be estimated or carried forward in any of the analyses.

A thorough description of the statistical methods as well as presentation of study results will be developed and finalized prior to locking the database. Deviations from the statistical analysis plan (SAP) will be documented in the clinical trial report.

Except where other software maybe deemed more appropriate, all analyses will be performed using SAS Version 9.4 statistical software (SAS Institute, Cary, NC).

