2.0 TRIAL SYNOPSIS

Title of Trial: An Open-Label, Dose Escalation Study to Assess the Safety, Pharmacokinetics

and Pharmacodynamic Signals of DUR-928 in Patients with Alcoholic Hepatitis.

Sponsor: DURECT Corporation

Phase of

Development: Phase 2a

Objectives and Primary Endpoints:

- Assess the safety and tolerability of DUR-928 in patients with alcoholic hepatitis (AH) as determined by the absence of suspected unexpected serious adverse reaction (SUSAR).
- 2. Determine the pharmacokinetics (PK) of DUR-928 in patients with AH
- 3. Assess the pharmacodynamic signals of DUR-928 in patients with AH as determined by:
 - a. Biochemical: Improvement in liver biochemistry, MELD score, and the drivers of the MELD score individually (INR/sCr and bilirubin) at Day 7 and Day 28 and Lille score at Day 7
 - b. Biomarkers: improvement of biomarkers PPD/CCI

Trial Design:

The proposed study is An Open-Label, Dose Escalation Study to Assess the Safety, Pharmacokinetics and Pharmacodynamics signals of DUR-928 in Patients with AH. DUR-928 will be administered in PPD/CCI by slow intravenous infusion over 2 hrs PPD/CCI until entire dose is given at Day 1 and Day 4. If a patient meets the hospital discharge criteria prior to the 2nddose, the patient will receive only one dose of DUR-928 instead of 2 doses.

[figure not shown]
Trial Rationale:

The study will be conducted in 2 Parts using a staggered parallel design. Part A will include patients with MELD scores of 11-20, and Part B will include patients with MELD of scores 21-30.

Within each Part, the study will be conducted using a starting dose level of 30 mg with sequential dose escalation following review of safety and PK results of the prior dose level by the sponsor, the principal investigators and the medical monitor. The planned subsequent doses of DUR-928 after the starting dose are 90 mg and 150 mg.

Patients with a MELD score of 21-30 (Part B) receiving the 30 mg dose level will only be enrolled once safety review of the 30 mg dose of DUR-928 in

patients with MELD score 11-20 (Part A) has been completed. The subsequent dose escalation in Part B will not proceed until the sponsor, the principal investigators, and the medical monitor complete the review of safety and evaluate PK results of the 30 mg dose level and determine it is safe to do so.

If no SUSAR is observed and PK results are satisfactory, dose escalation to the next dose cohort will proceed. All patients will be followed up to Day 28.

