Treatment emergent AEs will be listed and summarized by dose level. All AEs reported in this study will be coded using the current Medical Dictionary for Regulatory Activities (MedDRA). The overall incidences of AEs and SAEs in system organ class (SOC) and preferred term will be tabulated by dose level. In addition, incidence rates (frequencies and percentages) will be broken down by severity and/or relationship to study drug. Treatment emergent changes from baseline in clinical laboratory tests, ECG and vital signs will be derived by dose level.

Pharmacokinetics:

Plasma concentration data of DUR-928 from each patient will be used to calculate relevant PK parameters determined using a standard linear/log-trapezoidal rule non-compartmental method with an appropriate PK data analysis program.

PK parameters for DUR-928 will be summarized by dose group and Part A or B

using descriptive statistics.

Method and Timing:

PPD/CCI

Test drug, dosage and mode of administration:

DUR-928 at 30, 90 and 150 mg diluted as per the protocol in and infused over 2 hrs.

Refer to Section 7.1.1 for detailed instructions.

Comparator, dosage and mode of

administration: N/A

Power Calculations: No formal sample size estimates were performed. The number of patients

[figure not shown]
planned for this study is consistent with trials of this design and objectives.

(See Section 11.2).

Schedule of Events: Refer to Table 1 below.

Table 1: Schedule of Events

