5.0 CURRENT TRIAL

5.1 Trial Objectives and Primary Endpoints

- 1. Assess the safety and tolerability of DUR-928 in patients with AH as determined by the absence of SUSARs.
- 2. Determine the PK of DUR-928 in patients with AH.
- 3. Assess the pharmacodynamic signals of DUR-928 in patients with AH as determined by:
 - a. Biochemical: Improvement in liver biochemistry, MELD score, and the components of the MELD score individually (INR/sCr and bilirubin) at Day 7 and Day 28 and Lille score at Day 7
 - b. Biomarkers: improvement of biomarkers PPD/CCI

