8.0 ASSESSMENT OF EFFICACY

8.1 Efficacy Assessments

Change in MELD score and the components of the MELD score individually (INR/sCr and bilirubin), Lille score, biochemistry and biomarkers.

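### Safety and pharmacodynamic summaries by dose level permit pooling of Parts A and B, although PK is summarised by dose and Part

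*Combined protocol and SAP*

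**What the plan says.** **Grouping of summaries.** The safety paragraph of the synopsis (section 2.0) says: "The overall incidences of AEs and SAEs in system organ class (SOC) and preferred term will be tabulated by dose level". It adds: "Treatment emergent changes from baseline in clinical laboratory tests, ECG and vital signs will be derived by dose level". Section 11.5 says: "Categorical variables will be summarized by DUR-928 dose level using the ITT analysis set as counts and percentages". Continuous variables are to be summarised by treatment cohort unless specified otherwise, and a parenthesis equates that term with the DUR-928 dose levels. None of these sentences mentions Part.

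**What the Parts are.** Section 5.2 puts MELD 11-20 in Part A and MELD 21-30 in Part B. Section 7.1.1 lists cohorts 1A to 3A and 1B to 3B at 30, 90 and 150 mg and plans the same doses for both Parts. Section 11.1 describes the design as stratified by severity. Section 10.0 and the PK paragraph of the synopsis summarise PK by dose group and by Part. Section 5.3.3 gives 4 to 6 patients per cohort, three cohorts per Part and 24 to 36 patients in total.

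**Ranking of objectives (minor point).** The synopsis places safety, PK and pharmacodynamics together under "Objectives and Primary Endpoints", and section 5.1 uses a near-identical heading. Neither has a secondary tier. Item 3 in section 5.1 includes "the components of the MELD score individually (INR/sCr and bilirubin) at Day 7 and Day 28 and Lille score at Day 7". Section 11.5 reads differently: "The primary objective of this study is to assess dose-related safety and tolerability of DUR-928, with secondary objectives of assessing PK", and the sentence goes on to make evidence of potential efficacy secondary as well. Section 8.1 defines efficacy by the same measures as item 3: "Change in MELD score and the components of the MELD score individually (INR/sCr and bilirubin), Lille score, biochemistry and biomarkers".

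**The concern.** A dose level does not identify a Part, because both Parts are planned with the same three doses. A table by dose level can therefore combine patients from two non-overlapping severity bands. The protocol separates the bands for PK but does not say that it does so for safety, which 11.5 makes the primary objective, or for the pharmacodynamic measures.

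Two things are at stake in the reported results. First, an adverse event that occurs mainly in the sicker patients, or mainly in the less sick ones, is diluted by the other Part. Second, if the ratio of Part A to Part B patients differs between doses, the dose columns differ in severity before any drug effect, and a reader looking for a dose relation could mistake case mix for dose.

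The heading conflict is smaller. Read literally, 5.1 makes a Day 28 MELD result primary, while 11.5 makes it secondary.

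**Working it through.** **Inputs.** Patients per cohort: 4 to 6 (5.3.3). Cohorts: 3 per Part, 2 Parts (5.2, 5.3.3). Doses: the same three planned in each Part (7.1.1). MELD bands: 11-20 and 21-30 (5.2).

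**The plan's own total.** 3 × 2 × 4 = 24 and 3 × 2 × 6 = 36, which matches 5.3.3.

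**Size of a summary cell.**
- By Part and dose: 6 cells of 4 to 6 patients. One patient is 1/6 = 16.7% to 1/4 = 25.0%.
- By dose alone: 3 cells of 2 × 4 = 8 to 2 × 6 = 12 patients. One patient is 1/12 = 8.3% to 1/8 = 12.5%.

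**Dilution of an event confined to one Part.** If the event occurs only in Part B, pooled rate ÷ Part B rate = nB/(nA + nB).
- Lowest: 4/(6 + 4) = 0.40.
- Highest: 6/(4 + 6) = 0.60.
- Equal sizes: 0.50.

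The same range applies if the event occurs only in Part A. As an example (an assumption), take two affected patients in Part B, none in Part A, and equal cohort sizes. Part B shows 2/6 = 33.3% to 2/4 = 50.0%. The pooled table shows 2/12 = 16.7% to 2/8 = 25.0%. If the rates are the same in both Parts, pooling changes nothing.

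**Case mix between dose levels.** Suppose one dose has 4 Part A and 6 Part B patients, and another has 6 and 4. The documents give no mean MELD within a Part, so the means are assumed.

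| Assumed mean MELD, A and B | 4 A + 6 B | 6 A + 4 B | Gap |
|---|---|---|---|
| 15.5 and 25.5 (band midpoints) | (62 + 153)/10 = 21.5 | (93 + 102)/10 = 19.5 | 2.0 |
| 18 and 22 | (72 + 132)/10 = 20.4 | (108 + 88)/10 = 19.6 | 0.8 |
| 13 and 28 | (52 + 168)/10 = 22.0 | (78 + 112)/10 = 19.0 | 3.0 |

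These are the most uneven mixes that 4 to 6 patients per cohort allows; with equal Part sizes at every dose the gap is zero. The gap is in MELD at entry. The documents give no basis for saying how much of it would carry into change in MELD or the Lille score.

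**Limit of the counts.** Section 14.4.1 replaces patients who discontinue before the 24-hour PK sample. Section 11.4 keeps every dosed patient in the ITT set, so ITT cells may be somewhat larger than 4 to 6.

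**Heading conflict.** MELD, INR, sCr and bilirubin at two visits make 4 × 2 = 8 results, and Lille at Day 7 makes 9. If INR/sCr is read as one item, the count is 3 × 2 + 1 = 7. These are the named pharmacodynamic results that 5.1 heads as primary and 11.5 ranks as secondary. The count describes labels only.

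**The case against.** The strongest reply is that the text permits pooling but does not order it. Section 11.5 uses the term treatment cohort for continuous variables, and 7.1.1 defines six Part-specific cohorts, so that sentence can be read as already separating the Parts. This stands for the continuous variables, although the parenthesis pulls the other way. It does not help the categorical and adverse-event sentences, which say dose level only.

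The second reply is that the safeguards lie elsewhere. The synopsis has treatment-emergent adverse events listed as well as summarised, and 24 to 36 patients can be read line by line. That is fair, although the visible text does not say that the listing identifies Part. Escalation runs within each Part after review of the previous cohort (5.2, 7.1.1). A reader might infer that pooling could hide a Part B signal from the escalation decision. The documents do not support that, because those decisions do not rest on the pooled end-of-study tables.

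On the heading, 11.5 is the only text that ranks the objectives, and it does so plainly. A reader might infer that MELD and Lille are co-primary and raise a multiplicity problem. That does not follow: the analyses are descriptive and no formal sample size calculation was made (11.2, 11.5), so there is no error rate to inflate.

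Two further inferences also go too far. Section 8.2 calculates MELD at both screening and Day 1 pre-dose, and the visible text does not name one as baseline. That is ordinary SAP content: 11.4 defers further analysis details to the SAP, whose text is not in the document supplied, so the gap cannot be called a defect. Nor does finalising methods before database lock show that choices will follow the data. Section 11.5 commits to that deadline, and 11.5 and 11.7 require deviations to be documented, with reasons under 11.7. An earlier deadline would be a preference.

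**Conclusion.** The grouping point holds as a worthwhile, inexpensive improvement. The safety and categorical sentences allow tables that mix MELD 11-20 with MELD 21-30, in a design that the protocol itself calls stratified and for which it already separates PK by Part. At the planned cohort sizes, an event confined to one Part would appear at 40% to 60% of its rate there. An uneven mix could separate two dose levels by 0.8 to 3.0 MELD points at entry under the assumed Part means.

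These figures rest on 4 to 6 patients per cohort, on the same three doses being used in both Parts, and on the tables actually being pooled. The SAP may specify otherwise. The consequence is confined to how final results are presented and read; no error rate, sample size or escalation decision changes.

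The heading mismatch is real but editorial. Correcting it aligns labels and alters no result.

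**What to change.** In section 11.5 and in the statistics text of the synopsis, state:

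*Safety and pharmacodynamic summaries are presented by Part and dose, as for PK in section 10.0; any table pooled by dose level is supplementary.*

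In the synopsis and section 5.1, label safety as primary and PK and pharmacodynamics as secondary, to agree with 11.5.

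Both are wording changes and add no patients, visits or procedures. The real cost is sparser cells, in which one patient moves a percentage by 16.7 to 25.0 points instead of 8.3 to 12.5. Keeping the pooled table as a supplement, and showing counts beside percentages as 11.5 already requires, offsets most of that.

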5.2 Trial Rationale and Design

The study will be conducted in 2 Parts using a staggered parallel design. Part A will include patients with MELD scores of 11-20, and Part B will include patients with MELD of scores 21-30.

Within each Part, the study will be conducted using a starting dose level of 30 mg with sequential dose escalation following review of safety and PK results of the prior dose level by the sponsor, the principal investigators and the medical monitor. The planned subsequent doses of DUR-928 after the starting dose are 90 mg and 150 mg.

Patients with a MELD score of 21-30 (Part B) receiving the 30 mg dose level will only be enrolled once safety review of the 30 mg dose of DUR-928 in patients with MELD score 11-20 (Part A) has been completed. The subsequent dose escalation in each Part will not proceed until the sponsor, the principal investigators, and the medical monitor complete the review of safety and evaluate PK results of the 30 mg dose level and determine it is safe to do so.

If no SUSAR is observed and PK results are satisfactory, dose escalation to the next dose cohort will proceed. All patients will be followed up to Day 28.

Figure 1: Trial Schema

5.3 **Population**

[figure not shown]
Patients with AH will be enrolled at clinical sites in the US. The target number of participants to complete the study is 24-36. During the trial, patients should receive standard of care as determined by their PI.

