10.0 PHARMACOKINETICS

Plasma concentration data of DUR-928 from each patient will be used to calculate relevant pharmacokinetic parameters determined using standard non-compartmental method with linear/log-trapezoidal rule utilizing an appropriate pharmacokinetic data analysis program.

Pharmacokinetic parameters, such as C_{max} , T_{max} , $T_{1/2}$, AUC_{0-last} , AUC_{inf} , CL, and V_d , for DUR-928 will be calculated and summarized by dose group and Part A or B using descriptive statistics.

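### Safety and categorical summaries are grouped by dose level with no split by Part A and Part B, and the grouping of continuous variables is unclear, although the design is stratified by MELD and PK is split by dose and Part

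*Combined protocol and SAP*

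**What the plan says.** Section 5.2 defines the strata: "Part A will include patients with MELD scores of 11-20, and Part B will include patients with MELD of scores 21-30". Section 11.1 describes the design as stratified by disease severity. Sections 5.3.3 and 7.1.1 set out three dose cohorts in each Part, named 1A-3A and 1B-3B, with the same dose levels planned in both.

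The stated groupings are:

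- PK, synopsis: "PK parameters for DUR-928 will be summarized by dose group and Part A or B". Section 10.0 repeats it: parameters "will be calculated and summarized by dose group and Part A or B using descriptive statistics".
- Adverse events, synopsis: "Treatment emergent AEs will be listed and summarized by dose level", and "The overall incidences of AEs and SAEs in system organ class (SOC) and preferred term will be tabulated by dose level".
- Laboratory, ECG and vital signs, synopsis: "Treatment emergent changes from baseline in clinical laboratory tests, ECG and vital signs will be derived by dose level".
- Categorical variables, Section 11.5 and synopsis: "Categorical variables will be summarized by DUR-928 dose level using the ITT analysis set as counts and percentages".
- Continuous variables, Section 11.5 and synopsis: "continuous variables will be summarized by treatment cohort (DUR-928 dose levels) using the ITT analysis set".

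Only the PK sentences name Part. The one form of pooling that the protocol announces and justifies is across centers. Sections 11.4 and 11.5 leave further analysis detail and the presentation of results to a SAP to be finalized before database lock.

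**The concern.** Section 11.5 makes dose-related safety and tolerability the primary objective, and dose-related evidence of potential efficacy a secondary one. A column defined by dose alone holds patients from both MELD strata. That can mislead in two ways.

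The first is dilution. A safety signal confined to one Part appears at roughly half its rate, because the other Part fills the denominator. The second is mixing. If the A:B ratio differs between doses and the Parts differ in background rate, part of an apparent dose trend is really a difference in severity.

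For continuous variables the text does not settle the grouping. A cohort in Sections 5.3.3 and 7.1.1 is a dose within a Part, which gives six groups; the bracketed gloss in Section 11.5 points to three. MELD change falls under that sentence. The synopsis also groups laboratory and vital-sign changes, which include continuous measures, by dose level, so the two places should agree.

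**Working it through.** **The plan's own count.** From Section 5.3.3: 2 Parts × 3 cohorts × 4 = 24 and 2 × 3 × 6 = 36, matching the stated 24-36. Grouped by dose this gives 3 columns of 8-12 completers; grouped by dose and Part, 6 columns of 4-6.

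The documents give no event rates, A-B gaps or numbers of replaced patients. All such values below are assumptions.

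**Dilution.** Pooled rate = (events in A + events in B) / (n in A + n in B).

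- 3/6 in Part B, 0/6 in Part A: 3/12 = 25%, against 50% in Part B.
- 2/4 in Part B, 0/6 in Part A: 2/10 = 20%, against 50% in Part B.

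**Mixing.** With no true dose effect, the false difference between two dose columns = (difference in Part B share) × (A-B gap), where Part B share = B/(A + B).

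- *All cohorts filled, 4-6 each:* lowest share 4/(6+4) = 0.40, highest 6/(4+6) = 0.60; largest difference 0.20.
- *Up to one replaced patient per cohort kept in the ITT set:* 4/(7+4) = 0.364 to 7/(4+7) = 0.636; difference 0.273.
- *Up to two:* 4/(8+4) = 0.333 to 8/(4+8) = 0.667; difference 0.333.
- *Only 1-3 Part B patients at a dose:* share 1/(6+1) = 0.143 to 3/(4+3) = 0.429; largest difference from a filled dose 0.60 − 0.143 = 0.457.
- *No Part B patients at a dose:* difference from a filled dose 0.40-0.60.

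The replacement cases arise because Section 14.4.1 replaces patients who discontinue before the 24-hour PK sample, while Section 11.4 keeps every dosed patient in the ITT set. The incomplete cases are possible because Part B starts after the Part A 30 mg safety review, escalation is conditional (Section 5.2), and the sponsor may stop the trial (Section 6.4).

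Largest false difference in percentage points (a range where Part B is absent):

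| Situation | Gap 10 | Gap 30 | Gap 50 |
|---|---|---|---|
| All cohorts filled | 2 | 6 | 10 |
| One replaced per cohort | 2.7 | 8.2 | 13.6 |
| Two replaced per cohort | 3.3 | 10.0 | 16.7 |
| Part B partly filled | 4.6 | 13.7 | 22.9 |
| Part B absent | 4-6 | 12-18 | 20-30 |

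Example: at assumed rates of 10% in Part A and 50% in Part B at every dose, 4A+6B shows (0.4 + 3.0)/10 = 34%, 6A+4B shows (0.6 + 2.0)/10 = 26%, and 6A alone shows 10%.

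**Cost of splitting.** With zero events, the one-sided 95% upper bound is 1 − 0.05^(1/n): 52.7% at n = 4, 45.1% at 5 and 39.3% at 6, against 31.2% at 8, 25.9% at 10 and 22.1% at 12.

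**The case against.** The strongest reply is that the protocol never says the Parts will be combined. It often uses dose level for a dose inside a Part, and Section 11.5 ties dose levels to treatment cohorts, which are Part-specific. A six-group reading is therefore available, and column layout can be settled in the SAP. That deferral is real and a split could still be added. But the PK sentences show that the protocol names Part where it wants the split, and a SAP that follows the other sentences literally would produce dose-only tables. The clause allowing other specification opens only the continuous-variable sentence.

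The consequences are also limited, and this stands. Results are descriptive, with no test or power to distort. Safety is judged by the absence of SUSARs, and whether any SUSAR occurred does not depend on column layout. Escalation is reviewed cohort by cohort within each Part. Part and cohort are assigned for every patient, so the split can be recovered later. On plan, mixing is small: only at a 50-point gap does it reach one patient in ten. The larger figures need replaced patients kept in the ITT set, or a Part B cohort that is absent or below the stated minimum of 4.

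Finally, splitting makes the cells sparse. That is fair, though the plan already accepts cells of 4-6 for PK.

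**Conclusion.** The concern holds and should be fixed. The stated grouping for adverse events, SAEs, laboratory tests, ECG, vital signs and categorical variables does not carry the design's severity strata, and the grouping of continuous variables has two readings. No stated number is wrong.

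Dilution is the main effect: a signal confined to one Part shows at 40-60% of its rate when all cohorts are filled. Mixing is minor on plan and becomes material mainly if Part B is incomplete. The same multipliers apply to MELD change only if continuous variables are in fact pooled by dose. The sizes rest on assumed rates and counts; the inconsistency with the PK grouping rests on the text alone. The effect is confined to how the final results are read.

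**What to change.** In Section 11.5 and the matching synopsis text, state that safety and PD variables are shown by dose within Part A and Part B (cohorts 1A-3A and 1B-3B), alongside pooled-by-dose columns. Replace the double-meaning term for the continuous-variable grouping with wording that names the six cohorts. Align the synopsis sentence on laboratory, ECG and vital-sign changes with it, and carry the same grouping into the SAP.

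The cost is wording and wider tables. No new data are needed, and the change can be made any time before database lock. The drawback is sparse cells, with zero-event upper bounds of 39-53% per cohort against 22-31% pooled, which is why both displays should be kept.
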